## 1.6 Background

Traumatic injury and massive uncontrollable hemorrhage are major public health problems in the United States. Despite rapid, significant, advances in medicine and technology, hemorrhage treatment has in many ways lagged behind other blood product therapies such as coagulation factors and plasma proteins. A systemic hemostatic agent has the potential to fill unmet medical needs in non-compressible bleeding such as internal hemorrhage or diffuse vascular bleeding. Thrombosomes® treatment, if proven safe and effective in human trials, could assist in the management of blood loss associated with trauma, uncontrolled internal bleeding, and/or non- compressible hemorrhage.

In July of 2016, Cellphire completed a clinical study under an exploratory IND in 15 subjects (Thrombosomes n=10 and Control n=5) who received ascending doses of either: 1) Thrombosomes ranging from 1/1,000 to 1/10 of the projected minimum effective dosage (~1.89 x 10^8 Thrombosomes particles per kg or 330 Thrombin Generation Potency Units (TGPU) per kg), or 2) Thrombosomes Control (the mixture of excipients used to stabilize Thrombosomes but without the platelet component). The highest dose achieved was 1.55 x 10^7 particles per kg which has the potential to produce 27 IU of thrombin in-vitro.

There were no serious adverse events (SAEs) including deaths or stopping rules met on study, no decrease of platelet count of 20% or more from baseline, and no clinically significant changes in platelet count (change of 5% from baseline combined with post-baseline result outside of normal ranges) that occurred during the study. No statistically significant differences were seen when comparing the changes in platelet count between baseline and post-infusion values for subjects in Thrombosomes and Control groups.

Although this study, and more specifically the individual treatment cohorts, contained a small number of subjects, which led to high variability in reported AEs, the frequency and nature of TEAEs reported in this study are consistent with AEs that are typically observed in a healthy volunteer population. Overall, no clinically significant abnormalities were reported after infusion of Thrombosomes, and the results were similar between the control and treated cohorts.

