## 1.7 Product Information & Indications for Use

Thrombosomes are a lyophilized product prepared from a pool of group O human platelets (collected from 5-10 donors) that are being developed for the treatment of uncontrolled hemorrhage. Each vial from each lot of Thrombosomes contains a mean of 1.7 x 10^9 Thrombosomes particles per ml and an associated activity of approximately 3400 TGPU per ml after rehydration with 10 ml of sterile water for injection. Based upon efficacy studies in a thrombocytopenic New Zealand White Rabbit (NZWR) ear bleed model, the lowest observed efficacious dose was (1.89 x 10^8 particles per kg or 330 TGPU per kg). Refer to the *Investigator's Brochure* for additional information.

---

 National Highway Traffic Safety Administration Fatality Analysis Reporting System (FARS) 1975-2009 – <http://nhtsa.gov/FARS>

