### 1.9.2.2 Additional Hemostatic Therapy: All Cohorts

This product is not expected to increase the platelet corrected count increment (CCI). The infusion of platelets for six hours prior and one hour after infusion of Thrombosomes is

restricted. However, at any time, if the patient's clinical bleeding remains unchanged or deteriorates with additional or worsening bleeding, the patient's physician(s) may transfuse the patient with blood products, hemostatic agents, or coagulation factors without limitation. The study patient will be followed for safety data for 30 (+2) days post-infusion of the dose of Thrombosomes.

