#### 2.1.2 Secondary Objective

The secondary objective of this study is to assess potential efficacy of Thrombosomes for managing bleeding in actively-bleeding, thrombocytopenic patients.

Efficacy will be assessed within and across 3 sequentially enrolled patient cohorts, treated, respectively, at 3 escalating dose levels (see *Primary Objective* above). Post-infusion patterns showing stability or change toward clinical improvement in hematology measures will be used as preliminary indicators of possible product efficacy in bleeding management, and patterns in the receipt of transfused blood products will also be examined.

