**Table 1 – Patient Cohort Assignment, Target Dose, and Safety Margins**

Cohort	No. of Infusions	Target Mean Particles/kg	Target Mean TGPU/kg	Estimated Total Volume Infused 	Safety Margin 	
					Infused Particles/kg	Infused TGPU/kg
Cohort 1 (patients 1-8)	1	$9.45 \times 10^7$	165	4.1 mL	300	301
Cohort 2 (patients 9-16)	1	$1.89 \times 10^8$	330	8.2 mL	150	150
Cohort 3 (patients 17-24)	1	$3.78 \times 10^8$	660	16.4 mL	75	75

Abbreviation: TGPU, thrombin generation potency units.

 Estimated Total Volume Infused is based on a 70-kg patient and mean Thrombosomes concentration (across lots) of  $1.61 \times 10^9$  particles/mL with associated 2,800 TGPU/mL. Doses will be adjusted by patient weight in order to maintain the target Thrombosomes particle count per kg of patient body weight. Formula: Total Volume Infused in mL = ([patient weight in kg] x [desired dose in particles/kg or TGPU/kg, specific for the cohort]) ÷ Thrombosomes particles/mL or TGPU/mL provided with the specific lot of Thrombosomes. Example for Cohort 1: 4.1 mL = ([70 kg] x [ $9.45 \times 10^7$  particles/kg]) ÷  $1.61 \times 10^9$  particles/mL.

 Safety margins are based on the single acute toxicity study in New Zealand white rabbits (see CSP Section 1.7).

Written informed consent will be obtained from patients who are either actively bleeding or at risk of bleeding within 4 weeks following screening. Patients who are actively bleeding and determined through screening assessments to meet eligibility criteria for study participation will be immediately scheduled for infusion with Thrombosomes to occur within 4 days of screening. Patients who are not actively bleeding during screening but are at risk for bleeding within 4 weeks, based on medical history and projected clinical course, will be monitored for bleeding. If bleeding begins within 4 days (+6 hours), complete rescreening will not be necessary, but updated WHO bleeding assessment and complete blood count (CBC) tests will be required for determination of eligibility. If bleeding begins >4 days later but within 4 weeks of initiation of screening, rescreening (inclusive of all original screening assessments) will be necessary for

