## 9.1 Clinical Laboratory Assessments

Laboratory assessments to be used in efficacy analyses will include select hematology measures (hemoglobin, hematocrit, and platelets). Within a single table for each of 2 populations (Safety and Evaluable), the numbers and percentages of patients will be presented by categorized patterns of post-infusion change, including clinical improvement, stability/no change, and clinical worsening, for each of 2 post-infusion timeframes (infusion through the 24-hour post-infusion visit and infusion through the Day-6 visit). For each patient, categorization will require consideration of all measurements recorded across all time-points within the timeframe. For each hematology measure, clinical improvement and worsening will be defined as shown below. The category of stability/no change will apply by default when, for an individual patient, neither improved nor worsened conditions have been observed following infusion. When both improved conditions and worsened conditions have been distinctly observed at different time-points, the patient will fall into the category of clinical improvement.

Clinical improvement will be defined by:

- Hemoglobin increase of 1 g/dL
- Hematocrit increase of 3%
- Platelet count increase of 5,000/ $\mu$ L

Clinical worsening will be defined by:

- Hemoglobin decrease of 1 g/dL
- Hematocrit decrease of 3%
- Platelet count decrease of 5,000/ $\mu$ L

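### A platelet rise of 5,000/µL is scored as possible efficacy, although the protocol expects no rise in the platelet increment and the infused platelet-derived particles, if counted, would push the score up in order of dose

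*SAP*

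**What the plan says.** SAP 2.1.2 sets out how possible efficacy will be read, within and across the three dose levels: stability or "change toward clinical improvement in hematology measures will be used as preliminary indicators of possible product efficacy in bleeding management". SAP 2.2.2 makes the matching endpoint the number of patients with either stability or improvement, and an intermittent change is enough.

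SAP 9.1 supplies the rules for hemoglobin, hematocrit and platelets. For platelets, improvement is "Platelet count increase of 5,000"/µL and worsening is "Platelet count decrease of 5,000"/µL. All readings in each of two windows are used (infusion to the 24-hour visit, and infusion to the Day 6 visit). A patient who meets both rules at different times is classed as improved. The three categories are tabulated separately by cohort in Tables 14.2.1.1 and 14.2.1.2. The schedule (SAP Table 2, Protocol Table 4) includes blood counts at 1 h and 6 h, so these enter both windows.

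On the product, Protocol 1.7 states: "Thrombosomes are a lyophilized product prepared from a pool of group O human platelets". Protocol 1.9.2.2 states: "This product is not expected to increase the platelet corrected count increment (CCI"). Neither document says whether a blood analyzer counts the particles as platelets, what share stays in circulation, or for how long.

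**The concern.** The platelet category is offered as a sign that the product helps to manage bleeding. The protocol gives no reason to expect a platelet rise from it, and the product is platelet-derived, so the measurement may partly record the infusion.

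The same 5,000/µL threshold applies to doses that double from cohort to cohort. If any fraction of the particles is counted, the push toward improvement and away from worsening doubles too. A product with no effect on bleeding could then show improvement rising with dose, and dose is the comparison that SAP 2.1.2 makes. Because one transient early rise is enough and improvement overrides worsening, the 1 h and 6 h counts can settle a patient's category. Protocol 1.9.1 says that the data will support the design of later protocols, so a dose-ordered artefact could be carried forward.

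**Working it through.** **Inputs.** Target doses are 9.45×10⁷, 1.89×10⁸ and 3.78×10⁸ particles/kg, and the mean concentration is 1.61×10⁹ particles/mL (SAP Table 1). The thresholds are ±5,000/µL (SAP 9.1). The top dose in the earlier human study was 1.55×10⁷ particles/kg (Protocol 1.6). Blood volume is not in the documents; I assume 70 mL/kg, with a range of 60–80. The SD of platelet change is also not given and is assumed below.

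**The plan's own figure.** Volume = weight × dose ÷ concentration. For 70 kg, Cohort 3 is 70 × 3.78×10⁸ ÷ 1.61×10⁹ = 16.43 mL, against 16.4 mL stated. Cohorts 1 and 2 give 4.11 and 8.22 mL, against 4.1 and 8.2. The dose inputs are read correctly.

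**Largest possible particle contribution.** Particles per µL of blood = (particles/kg) ÷ (blood volume in mL/kg × 1,000). Weight cancels.

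| Dose | 60 mL/kg | 70 mL/kg | 80 mL/kg |
|---|---|---|---|
| Cohort 1 | 1,575 | 1,350 | 1,181 |
| Cohort 2 | 3,150 | 2,700 | 2,362 |
| Cohort 3 | 6,300 | 5,400 | 4,725 |
| Earlier study, top dose | 258 | 221 | 194 |

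These are ceilings: every particle circulating and every one counted. The documents also describe the Cohort 3 dose in other ways, which do not agree and should be reconciled. At 70 mL/kg, about 20 mL in a 70 kg patient gives 6,571/µL (at 1.61×10⁹/mL) to 6,939/µL (at 1.7×10⁹/mL). The dose of 660 TGPU/kg at 3,400 TGPU/mL and 1.7×10⁹/mL gives 4,714/µL.

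**Can product alone reach +5,000?** In Cohort 3 the fraction needed is 5,000 ÷ 5,400 = 93% at 70 mL/kg and 5,000 ÷ 6,300 = 79% at 60 mL/kg. Above 75.6 mL/kg it cannot (3.78×10⁸ ÷ 5,000 ÷ 1,000 = 75.6). Cohorts 1 and 2 cannot reach it anywhere in the range.

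**Effect on the categories.** Take one reading, no true change, a normal distribution, an assumed SD of 4,000/µL, counted fraction f and ceiling c at 70 mL/kg. Then P(improvement) = 1 − Φ((5,000 − f·c)/SD) and P(worsening) = Φ((−5,000 − f·c)/SD). For example, Cohort 3 with f = 1 gives 1 − Φ(−400/4,000) = 54%.

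| Counted fraction | Improvement, Cohorts 1 / 2 / 3 | Worsening | Stable or improved |
|---|---|---|---|
| None | 11 / 11 / 11% | 11 / 11 / 11% | 89 / 89 / 89% |
| Half | 14 / 18 / 28% | 8 / 6 / 3% | 92 / 94 / 97% |
| All | 18 / 28 / 54% | 6 / 3 / 0.5% | 94 / 97 / 99.5% |

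The ordering does not depend on this SD. With all counted, improvement is 7 / 18 / 56% at SD 2,500, 23 / 32 / 53% at SD 5,000 and 36 / 41 / 52% at SD 10,000. With none counted it is 2%, 16% and 31% in every cohort. SAP 9.1 uses several readings per window, so these figures show direction and rough size; they are not the planned endpoint's rates.

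**Check on a simple correction.** Suppose the ceiling is subtracted from every count when in fact nothing is counted (SD 4,000). In Cohort 3 a reading is then called worse if the true change is +400 or less: Φ(400/4,000) = 54%, against a correct 11%. Improvement falls to 1 − Φ(10,400/4,000) = 0.5%. Cohorts 1 and 2 show 18% and 28% worsening. This is the same artefact with its sign reversed.

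**The case against.** The strongest objection is that nothing in the documents says that the particles circulate or are counted, and Protocol 1.9.2.2 expects no increase in the platelet increment. Part of this stands: the counted fraction is unknown, 5,400/µL is a ceiling that rests on an assumed blood volume, and if the fraction is zero there is no artefact. But the protocol's expectation does not rescue the scoring rule. If it is right, a platelet rise is not an expected product effect and should not be scored as a sign of efficacy.

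A reader might infer that the earlier human study settles the matter, because Protocol 1.6 reports: "No statistically significant differences were seen when comparing the changes in platelet count between baseline and post-infusion values". It does not, since that study's top dose could add at most about 221/µL (194–258). Equally, the protocol does not say that its expectation rests on that study, and it refers to an Investigator's Brochure that is not available here. The basis of the expectation is unknown, not absent.

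The endpoint in SAP 2.2.2 combines stability with improvement. In the illustration it differs by only about 5 percentage points between Cohorts 1 and 3, or 0.05 × 8 = 0.4 of a patient. This stands. The larger shifts concern the separately tabulated categories. Those are descriptive: no between-cohort test is planned on them.

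A reader might also infer that the rule hides platelet falls from safety monitoring. The documents do not support that. SAP 9.1 is an efficacy analysis. Safety review under SAP 8.3 has platelet summaries by visit, abnormal and shift tables, individual plots and listings, although platelets are not among the measures in the hematology change-from-baseline table. Counted particles would offset those raw values too, but changing SAP 9.1 would not alter them.

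**Conclusion.** The point holds as a limit on how the efficacy table may be read. SAP 2.1.2 and 9.1 treat a platelet rise as possible efficacy in bleeding management, which Protocol 1.9.2.2 gives no ground to expect, and the particle load may itself add to the count in proportion to dose. The ceiling is about 1,350, 2,700 and 5,400/µL at an assumed 70 mL/kg (Cohort 3: 4,725–6,300 over 60–80 mL/kg), against a threshold of 5,000/µL. Any counted fraction shifts the improvement and worsening categories in order of dose.

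It would go too far to say that Cohort 3 patients will cross the threshold on product alone, or that a false dose-response will occur. The first needs about 93% of particles circulating and counted at 70 mL/kg, and the second depends on a fraction that the documents do not give. Platelets are also one of three measures in one of several secondary endpoints.

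**What to change.** In SAP 9.1 and Tables 14.2.1.1–14.2.1.2, keep the unadjusted platelet row and add two rows:

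- (a) the same classification using only counts at 24 h or later;
- (b) a sensitivity row for the 1 h and 6 h counts, with the cohort's maximum particle contribution subtracted (target particles/kg ÷ stated blood volume). Label it as a bound. It should not act as a pass/fail gate and should not be used to classify worsening, because full subtraction creates the reverse artefact when few particles are counted.

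In SAP 2.1.2, state that a platelet rise on its own is not read as evidence of product efficacy in bleeding management, in line with Protocol 1.9.2.2. Also state that a dose trend in the platelet category is interpreted only if its direction is the same in the unadjusted, bounded and 24 h-or-later rows; otherwise its direction is reported as undetermined. If the sponsor knows whether its counting method separates product from native platelets, SAP 9.1 should say so.

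The cost is SAP wording and two table rows, with no new data. A genuine early rise will be read more cautiously. Row (a) is more exposed to platelet transfusion, which Protocol 1.9.2.2 allows when bleeding persists or worsens, so it should be read beside the transfusion tables in SAP 9.2. Nor is row (a) shown to be free of product, because the documents do not say how long particles circulate. The change does not bear on safety monitoring.

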## 2.2 Study Endpoints

### 2.2.1 Primary Endpoints

Several primary endpoints will be quantified per patient cohort (i.e., by dose level), as well as overall (i.e., across all 3 dose levels):

- Overall frequency of (and number and percentage of patients who experience) TEAEs and TESAEs, including serious adverse drug reactions and treatment-related events specifically defining the study's suspension and stopping rules (i.e., thromboembolic events, acute lung injury, anaphylaxis, and death).
- Numbers and percentages of patients by highest WHO bleeding severity grade at baseline and post-baseline time-points, by highest severity grade at post-baseline time-points relative to baseline (allowing for assessment of shift), by both highest severity grade and bleeding site at baseline and post-baseline time-points, and by indication of a maximum severity grade  $\geq 2$  across bleeding sites at post-baseline time-points.
- Numbers and percentages of patients by grade-level change in WHO bleeding severity (e.g., -2, -1, 0, +1, +2, +3) from baseline to post-baseline time-points for the patient's most severe bleeding site at baseline, by indication of increased bleeding severity from baseline to post-baseline time-points for the patient's most severe bleeding site at baseline, and by indication of newly-developed bleeding sites from baseline to post-baseline time-points.
- Statistics describing (and/or graphics showing) central tendency and variability in coagulation, hematology, and serum chemistry measures across patients at baseline and post-baseline time-points, allowing for assessment of directional change in measures over time.
- Number and percentage of patients who shift from normal or clinically non-significant abnormal findings to clinically significant abnormal findings in coagulation, hematology, or serum chemistry measures between baseline and post-baseline time-points.
- Statistics describing central tendency and variability in vital signs, oxygen saturation (per pulse oximetry), and select 12-lead electrocardiogram (EKG) measures across patients at baseline and post-baseline time-points.
- Number and percentage of patients who shift in category of overall EKG interpretation from normal or clinically non-significant abnormal to clinically significant abnormal between baseline to post-baseline time-points.

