### ***1.9.3 Assessment of Bleeding: Using WHO Bleeding Score***

Use of the WHO (World Health Organization) Bleeding Assessment will provide a standardized approach, across multiple clinical sites, in order to determine study eligibility, for assessing a patient's bleeding during the clinical trial, and for assessing the effect of Thrombosomes (if any) on bleeding. Study personnel conducting the assessment will be trained on the assessment and will be authorized by the PI to perform the assessment. This authorization will be documented on the Authorities and Responsibilities Log. The location of bleeding for all bleeding sites will be assessed by WHO grade during study at screening, (re-screening, if applicable) baseline, 1 hour, 6 hours, 24 hours post-infusion and 6 days post-infusion. In some instances, a bleeding site may not be able to be reassessed post-infusion due to the need for an invasive procedure or other procedure that would add additional risk for the subject. The protocol does not require subjects to undergo medically unnecessary procedures (or risks) only in order to perform post-infusion WHO bleeding assessments. Subjects who are transfused with red cells to treat anemia due to their underlying disease (and not because of bleeding) will not be assessed as having WHO grade 3 bleeding. Anemia from underlying disease will be designated if there is evidence of bone marrow suppression indicated by at least two of the following: leukopenia, thrombocytopenia, or reticulocytopenia; and absence of WHO grade 2 bleeding in the prior 24 hours. For designation of WHO grade 3 bleeding, red cell transfusion must be specifically related to treatment of bleeding within 24 hours of onset of bleeding. (see Table 4. Schedule of Events for timing of WHO bleeding assessments). The same person must perform assessment of pre-infusion and 1-hour post-infusion time points.

To assess bleeding and determine the WHO Bleeding Score, the patient will be interviewed, a physical examination will be performed, and the patient's chart will be reviewed. The WHO Bleeding Score will be determined using Appendix A- Modified WHO Bleeding Score.

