### 8.2 WHO Bleeding Severity Scores

Within multiple tables, the numbers and percentages of patients will be presented by highest WHO bleeding severity score (no bleeding/grade 0, grade 1, grade 2, grade 3, or grade 4), with "highest severity score" defined as the score associated with the most severe bleeding site (given documentation of multiple sites) for the nominal time-point of interest. This distribution of highest WHO bleeding severity scores not only will be presented by nominal time-point but also will be presented by post-baseline time-points relative to baseline time-point (to allow for assessment of shift) and by both bleeding site and time-point. Differences between patient cohorts (dose levels) in the proportion of the study population showing grade 2 or higher bleeding severity for the most severe bleeding site will be tested for statistical significance per time-point using Fisher's exact test, with results displayed in a single table. To facilitate visual examination of trends, 1 or more of the summaries described above may be presented within supplementary clustered bar charts or line chart overlays.

The numbers and percentages of patients will also be presented by grade-level change in WHO bleeding severity (-2, -1, 0, +1, +2, and +3) from baseline to post-baseline time-points for the patient's most severe bleeding site at baseline, by indication of increased bleeding severity from baseline to post-baseline time-points for the patient's most severe bleeding site at baseline, and by

indication of development of new bleeding sites from baseline to post-baseline time-points. Lastly, the details of all WHO bleeding assessments will be presented in a patient-level data listing. To facilitate, within this listing, visual examination of possible post-infusion changes in bleeding severity or number of bleeding sites as associated with protocol-defined windows for the timing of infusion relative to screening (i.e., within 24 hours [as stipulated in CSP v1.1] vs. within 4 days [as stipulated in CSP v2.0+]), the data listing will be sorted first by the screening assessment dates of patients and then, within individual patients, by assessment date.

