### **14.3.3 WHO Bleeding Severity Scores**

Table 14.3.3.1	Summary of Highest WHO Bleeding Severity Scores by Visit – Safety Population
Table 14.3.3.2	Summary of Highest WHO Bleeding Severity Scores by Bleeding Site and Visit – Safety Population
Table 14.3.3.3	Shift from Baseline in Highest WHO Bleeding Severity Score – Safety Population
Table 14.3.3.4	Between-Cohort Differences in WHO Bleeding Severity Scores of at least Grade 2 – Safety Population
Table 14.3.3.5	Post-Infusion Grade-Level Changes in Bleeding Severity Score for Most Severe Bleeding Site at Baseline – Safety Population
Table 14.3.3.6	Subjects with Increased Post-Infusion WHO Bleeding Score for Most Severe Bleeding Site at Baseline – Safety Population
Table 14.3.3.7	Subjects with Post-Infusion Development of New Bleeding Sites – Safety Population

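### In a patient bleeding at Grade 2 at one site and Grade 1 at another, worsening at the second site is neither an increase nor a new site, and a rise from Grade 1 to 2 appears in no patient-level change table

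*SAP*

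**What the plan says.** SAP 2.2.1 lists several bleeding summaries as primary endpoints, and SAP 8.2 gives the methods. They fall into two groups.

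- **Following one site.** Grade-level change (Table 14.3.3.5) and the increase indicator (Table 14.3.3.6) track only the site that was worst at baseline, called the index site below. SAP 2.2.1 counts patients "by indication of increased bleeding severity from baseline to post-baseline time-points for the patient's most severe bleeding site at baseline", and the planned table carries the same limit in its title: "Subjects with Increased Post-Infusion WHO Bleeding Score for Most Severe Bleeding Site at Baseline". Beside it stands an "indication of development of new bleeding sites from baseline to post-baseline time-points" (Table 14.3.3.7).
- **Using all sites.** The highest grade is chosen afresh at each visit as "the score associated with the most severe bleeding site (given documentation of multiple sites) for the nominal time-point of interest". It is tabulated by visit (Table 14.3.3.1), as a shift from baseline (Table 14.3.3.3), and as the proportion at Grade 2 or higher (Table 14.3.3.4). Patients are also counted "by both highest severity grade and bleeding site at baseline and post-baseline time-points" (Table 14.3.3.2).

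When two sites tie for worst at baseline, SAP 8.2 follows the one with the higher grade at the first later visit where they differ.

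Protocol 1.9.3 provides the data for every site: "The location of bleeding for all bleeding sites will be assessed by WHO grade during study". Protocol 1.9.2 admits only Grade 1 (a subset) or Grade 2 bleeding, so the worst baseline grade is at most 2.

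**The concern.** The increase and new-site indicators look as if together they cover any worsening after infusion. They do not. A second site that was already bleeding at baseline, at a lower grade than the index site, belongs to neither. If it worsens, the patient is classed as not increased and as having no new site.

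SAP 2.1.1 names worsening of bleeding severity as an indicator for the primary safety objective, and Table 14.3.3.6 has the title a reader would turn to for it. With 8 patients per cohort, one patient classified differently moves a cohort percentage by 1/8 = 12.5 points.

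**Working it through.** The plan states no figure for this endpoint, so there is nothing to reproduce. The check applies the SAP 8.2 rules to every possible grade pattern.

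**Inputs.** Two sites, both bleeding at baseline at Grade 1 or 2 (Protocol 1.9.2); later grades 0 to 4 (SAP 8.2); one later visit; no third site. With no tie, the only possible baseline is index site 2, second site 1, written {2,1}.

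**Untied baseline {2,1}.**

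- The second site worsens if it reaches 2, 3 or 4, and the index site can then be at any of 0 to 4: 3 × 5 = 15 patterns.
- The index site has not risen if it is at 0, 1 or 2: 3 × 3 = 9 patterns. In all nine, neither the increase nor the new-site indicator fires.

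| Second site after | Index site after | Table 14.3.3.5 (change) | Table 14.3.3.6 (increased) | Table 14.3.3.7 (new site) | Table 14.3.3.3 (highest grade) |
|---|---|---|---|---|---|
| 4 | 2, 1 or 0 | 0, −1 or −2 | no | no | 2 to 4 |
| 3 | 2, 1 or 0 | 0, −1 or −2 | no | no | 2 to 3 |
| 2 | 2 | 0 | no | no | 2 to 2 |
| 2 | 1 | −1 | no | no | 2 to 2 |
| 2 | 0 | −2 | no | no | 2 to 2 |

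So 9 = 6 shown by the highest-grade shift + 3 shown by no patient-level change table. Two of those three are recorded as improvement at the index site. Counting either site as the index doubles the figures: 18 = 12 + 6, with 4 of the 6 recorded as improvement.

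**An example across two rows of Appendix A.** At baseline a patient has epistaxis lasting over 30 minutes (Grade 2, oral and nasal row) and microscopic blood in the urine (Grade 1, genitourinary row). Later the epistaxis is down to Grade 1 and the hematuria is visible (Grade 2). Table 14.3.3.5 records −1, Table 14.3.3.6 no increase, Table 14.3.3.7 no new site, and Table 14.3.3.3 no change. The proportion at Grade 2 or higher does not move either.

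**Tied baselines.** With one later visit no pattern is missed, because the tie rule picks the site that worsened. With two later visits, the tied site that was not selected stands above its baseline grade at the second visit in 565 patterns. The increase indicator does not fire in 240 of them, and the highest-grade shift shows all 240.

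**The two rules side by side.** From {1,1} to {1,2}, the tie rule follows the worsened site and the patient counts as increased. From {2,1} to {2,2}, the same one-grade rise at a site bleeding at baseline is not counted.

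**The case against.** The strongest case against is that the plan does not rest on Table 14.3.3.6 alone. The all-site summaries are primary endpoints in the same list, and no pattern in which a second site reaches Grade 3 or 4 escapes the highest-grade shift. That stands. A reader might infer that worsening at any other site goes uncounted in the plan; the documents do not support this. What remains is the rise from Grade 1 to 2. Table 14.3.3.2 includes it, but only as counts per site and visit, where one patient's rise can be offset by another's fall. The patient listing shows it case by case.

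A second objection is that the SAP does not define a site. Appendix A grades nose and mouth in one row, so if a site means a row, a nose-and-gum patient has a single site and no gap arises. That stands for such pairs, but sites in different rows are still affected.

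Third, little is decided on this table. It is descriptive. The one bleeding test in SAP 8.2 uses the all-site proportion at Grade 2 or higher, the suspension and stopping rules rest on SAEs, and the DMC tables in SAP Appendix 1 include no WHO summary. This limits the weight of the point without removing it.

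A reader might also infer a large bias toward improvement, since the followed site was chosen for being worst. The direction is plausible, but the documents do not support a size: it depends on how grades move between visits and on how many patients bleed at several sites, and neither is given. The highest grade can also fall with no drug effect.

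Finally, an any-site indicator is not neutral. The more sites a patient has at baseline, the more chances one will rise. Cohorts that differ in number of sites could then differ in rate without a dose effect. This is a good reason to add the row and not to replace the existing one.

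**Conclusion.** The gap is real and narrow. For an untied {2,1} baseline, the increase and new-site indicators miss nine of the 15 patterns in which the second site worsens. Six of the nine are recovered by Table 14.3.3.3, although Table 14.3.3.6 then classes as not increased a patient who reached Grade 3 or 4. The other three, all with the second site going from 1 to 2 while the index site does not rise, appear in no patient-level change table; two of them are tabulated as −1 or −2.

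This rests on two sites that the analysis treats as distinct and on no third site. Patients with one site are unaffected, and tied baselines never escape the highest-grade shift. The number of patients affected cannot be estimated from the documents. The point merits a cheap improvement to a primary safety summary; it does not invalidate the bleeding analysis.

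**What to change.** - In Table 14.3.3.6, keep the index-site row and add a row counting patients whose WHO grade is above baseline at any site that was bleeding at baseline, by visit. Add the same indicator to SAP 2.2.1 and 8.2, using the same unit of site as Table 14.3.3.2.
- State in SAP 8.2 that Tables 14.3.3.5 and 14.3.3.6 are to be read with Table 14.3.3.3. That table already gives the patient-level change in highest grade, so no further change table is needed.
- Report the number of sites bleeding at baseline by cohort, so that a difference in the any-site rate can be judged against it.

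The cost is one table row, a short baseline summary and a few sentences in the SAP. No new data are needed, because Protocol 1.9.3 already has every site graded. Protocol 1.9.3 also allows that some sites cannot be reassessed after infusion; the new row should treat such a site as missing at that visit.
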